4.2 Other Restrictions

None.

5 Reporting of Adverse Events

Adverse events will be recorded from the first dose of IMP administration through 30 days after administration of IMP and collected by observation and reporting. AEs will be elicited from subjects by asking questions regarding changes in the subject's status at each visit.

5.1 Definitions

5.1.1 Adverse Event

An AE is any untoward medical occurrence (whether or not considered to have a causal relationship to IMP) in a study subject administered an IMP. Therefore, an AE can be any unfavorable and unintended sign (including clinically significant laboratory finding), symptom, or disease temporally associated with the use of an IMP, whether or not related to the IMP.

However, signs and observations that are associated with clinical improvement (such as discharge of blood clots in urine), as judged by the investigator, will not be reported as AEs.

5.1.2 Adverse Drug Reaction

All noxious and unintended responses to an IMP related to any dose should be considered ADRs. The phrase “responses to an IMP” means that a causal relationship between the IMP and the AE is at least a reasonable possibility, that is, the relationship cannot be ruled out.

5.1.3 Serious Adverse Event

An SAE is any untoward medical occurrence that at any dose:

- Results in death.
- Is life-threatening (i.e., the subject was at immediate risk of death from the AE as it occurred. This does not include an event that, had it occurred in a more severe form or was allowed to continue, might have caused death).
- Requires inpatient hospitalization or prolongation of existing hospitalization.
- Results in persistent or significant disability/incapacity.
- Is a congenital anomaly/birth defect (in the child of a subject who was exposed to the study drug) or
- Is a medically important event or reaction:

Events that did not result in death or hospitalization but may, based on appropriate medical judgment, jeopardize the subject or require intervention, to prevent one of the outcomes in the definition of SAE listed above, should also be considered SAEs.

5.1.4 Assessment of Severity

The severity of all AEs and SAEs must be assessed according to the following categories:

- **Mild** – The AE/SAE is easily tolerated by the subject, causes minimal discomfort and does not interfere with everyday activities; or
- **Moderate** – The AE/SAE is sufficiently discomforting to interfere with normal everyday activities; or

- **Severe** – The AE/SAE prevents the subject from engaging in normal everyday activities.

The term “severe” is used to describe the intensity of a specific event. The event itself may be of relatively minor medical significance (such as a severe headache). “Severe” is not the same as “serious”, which is defined on subject/event outcome or action criteria usually associated with events that pose a threat to a subject/subject’s life or ability to carry out life functions. Seriousness is a medical term, while severity is a subjective term.

5.1.5 Assessment of Causality

The following 4-point scale will be used by the investigator to rate the relationship of the adverse event to the IMP:

- **Definitely related:** A clinical event (including laboratory test abnormality) occurring in a plausible time relationship to IMP administration and which cannot be explained by concurrent disease or other drugs or chemicals. The response to withdrawal of the drug (de-challenge) should be clinically plausible. The event must be definitively associated pharmacologically, using a satisfactory re-challenge procedure, if necessary; or
- **Probably related:** A clinical event (including laboratory test abnormality) with a reasonable time sequence to administration of the drug, unlikely to be attributed to concurrent disease or other drugs or chemicals, and which follows a clinically reasonable response on withdrawal (de-challenge). Re-challenge information is not required to fulfill this definition; or
- **Possibly related:** A clinical event (including laboratory test abnormality) with a reasonable time sequence to administration of the drug, but which could also be explained by concurrent disease or other drugs or chemicals. Information on drug withdrawal may be lacking or unclear; or
- **Not related:** An event for which sufficient information exists to conclude that the etiology of the event is unrelated to the IMP.

The degree of certainty with which an AE or SAE is attributed to treatment with IMP (or alternative causes, e.g., natural history of underlying diseases, concomitant therapy) will be determined by how well the event can be understood with regard to one or more of the following:

- Known pharmacology of the IMP;
- Reaction of similar nature being previously observed with this medication or class of medications;
- The event having often been reported in literature for similar medications as related; and/or
- There is a temporal relationship between IMP administration and the event.

Refer to the Investigator’s Brochure for all available relevant information about the IMP.

The investigators will assign causality at their respective sites during the study. The medical monitor responsible for the study will review the assigned causality for all AEs and SAEs prior to data-base lock. This assignment will be included in the study database and final study report.

5.2 Eliciting and Reporting Adverse Events

The condition of the patient will be monitored throughout the study. At each visit, AEs will be elicited using a standard non-leading question such as “*How have you been since the last visit / during the previous study period?*” AEs will also be elicited through the use of Subject Diary cards, which the investigator will review in detail with the subject at each visit, ensuring accuracy and completeness of entries recorded by the subject.

Any AE or ADR occurring during the study will be noted in detail on the appropriate pages of the eCRF. If the patient reports several signs or symptoms, which represent a single syndrome or diagnosis, the latter should be recorded in the eCRF. The investigator will grade the severity of all AEs or ADRs (mild, moderate or severe), the seriousness (non-serious or serious) and relatedness, as defined in Section 5.1.

In the event of clinically significant abnormal laboratory findings, the tests will be repeated and followed-up, as needed. Diseases, signs and symptoms, and/or laboratory abnormalities already existing before the first administration of IMP are not considered as AEs when observed at a later stage unless they represent a worsening.

The investigator should always provide detailed information concerning any abnormalities and the nature of, and reasons for any necessary action(s), as well as any other observations or comments, which are useful for the interpretation and understanding of the subjects’ AEs or ADRs.

5.3 Serious Adverse Event Reporting

All AEs must be evaluated as potential serious adverse events (SAEs). All AEs assessed as serious must be reported beginning from the time of first dose of IMP until 30 days post dose. SAEs must be followed until the event resolves, the event or sequelae stabilize, or it is unlikely that additional information can be obtained after demonstration of due diligence with follow-up efforts (i.e., the subject or investigator is unable to provide additional information or, the subject is lost to follow-up).

5.3.1 SAE Reporting to the CRO

All SAEs will be reported within 24 hours of the investigator becoming aware of the event to the Pharmacovigilance (PV) CRO Safety Department submitting the Safety Report 24/7 on the fax number below.

Toll Free Fax US: [name]

Toll Free Fax Norway: [name].

Full details of SAE reporting to the PV CRO will be defined in the Safety Management Plan. The telephone number for ITSI is [name] in US. Alternately any safety information can be sent via email to [contact].

It should be noted that reporting to the PV CRO Safety Department within 24 hours of awareness is required for all SAEs regardless of their causal relationship with the IMP.

The PV CRO Safety Department, together with the sponsor's medical monitor, will review all safety information/documentation and follow up with the investigative site to obtain any other required information. Follow-up information should be actively sought by the investigator and reported to the PV CRO Safety Department as it becomes available using the Safety Report.

The sponsor is responsible for reporting SAEs to IND/CTA under the oversight of the FDA and NMA (Norwegian Medicines Agency), respectively, as applicable.

5.3.2 Institutional Review Board/Ethics Committee

All AEs will be reported to the IRB/EC according to the guidelines of the IRB/EC. However, as a general guideline, IRBs/EC need to know about any AEs that are unexpected or of a greater severity than what is reported in the IB. Reporting is always required for all SAEs. Any new safety data (or other finding) that might affect an IRB/EC's judgments regarding their risks versus benefits analysis should always be reported to the IRB/EC. The sponsor and the CRA will assist the investigator in determining which events require reporting and in what timeframes.

5.3.3 Expedited SUSAR Reporting (Sponsor Responsibility)

The sponsor will submit a written IND Safety Report (i.e., completed FDA Form 3500A and/or CIOMS form) within 15 calendar days of receipt to the responsible review division of the FDA and the Norwegian Medicines Agency, as required, for any observed or volunteered SAE that is:

- 1) Suspected to be associated with the investigational drug or study treatment(s); and
- 2) Unexpected.

Any SUSARs that will be filed to the IND for the purpose of notifying FDA, and will be filed electronically via EudraVigilance for the purpose of notifying the Norwegian Medicines Agency.

In addition, if the event is fatal or life-threatening and meets the above criteria, a telephone or facsimile notification will be sent to the FDA as soon as possible, but no later than 7 calendar days after the sponsor's initial receipt, followed by a completed FDA Form 3500A within 15 calendar days after initial receipt.

Each IND Safety Report will be prominently labeled "IND Safety Report," and a copy will be provided to all participating site investigators.

For each written IND Safety Report, the sponsor will identify all previously submitted IND Safety Reports that addressed a similar adverse event experience and will provide an analysis of the significance of the newly reported adverse event in light of the previous, similar report(s).

If the results of the sponsor's follow-up investigation show that an adverse event that was initially determined to not require a written IND Safety Report does, in fact, meet the requirements for reporting, the sponsor will submit a written IND Safety Report as soon as possible, but in no event later than 15 calendar days after the determination was made.

Follow-up information to an IND Safety Report will be submitted to the applicable review division of the FDA as soon as the relevant information is available.

5.4 Pregnancy

Every effort must be made to avoid a pregnancy during the trial. Contraception should be used in accordance with Inclusion Criterion #6, and the techniques discussed at Screening should preferably not be changed during the course of the trial. A pregnancy test will be performed at Screening and at each study visit.

In case a subject becomes pregnant during the trial, she has to be withdrawn. Pregnancies occurring during the study after exposure to the IMP need to be reported. The pregnancy notification form has to be sent to the CRO Safety Department. Follow-up information on the outcome of both mother and fetus must also be reported.

5.5 Procedure for Breaking the Blind

This is not a blinded study.

5.6 Follow-up of Adverse Events

The responsible investigator will follow up each AE until it is resolved or until the medical condition of the patient has returned to baseline, and all relevant follow-up information has been reported to the sponsor.

6 Statistical Analysis

6.1 Datasets for Analysis

Safety population: Includes any subject who receives at least one dose of the IMP and provides safety data for at least one non-screening visit.

PK population: Includes subjects who have completed Segment 2 dosing and have provided sufficient samples for PK assessments.

Full Analysis Set (FAS): Includes any subject who receives at least 1 dose of the IMP and provided data for at least one post-baseline efficacy assessments.

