3.1 Overall Study Design

Approximately 15 subjects aged 2 to 80 years with hypoplasminogenemia will be enrolled to ensure a sample size of at least 10 PK-evaluable subjects. At least 2 pediatric subjects, aged 2 to 18 years, will be enrolled. An evaluable subject for PK is defined as a subject who completes Segment 2 of plasminogen replacement therapy (see below) of the study and provides at least 3 blood samples to measure trough plasminogen activity levels.

The study consists of a screening period and 3 segments as illustrated in Figure 1. Subjects who have documented individual PK profiles with the sponsor (e.g., due to participation in the previous Phase 1 study and received 6 mg/kg Plasminogen) do not need to undergo Segment 1 and can proceed directly to Segment 2.

Screening

Subjects will be screened for study eligibility within a period of no more than 21 days before the start of dosing. Subjects will enter either Segment 1 or 2, depending on the availability of their prior individual PK profile.

Segment 1

For subjects undergoing Segment 1, each will receive a single dose of 6.6 mg/kg Plasminogen IV infusion on Day -4. Blood samples for PK analysis will be drawn prior to infusion and subsequently through 96 hours after the infusion to establish individual PK profiles. The sample drawn prior to infusion will be used to measure the subject's baseline plasminogen activity and antigen as well as D-dimer levels. The last PK sample (96 hours post infusion) will be withdrawn on Week 1, Day 0, before the administration of the first dose in Segment 2. The resulting PK profile will be used to determine each subject's dosing interval in Segment 2.

Segment 2

Based on individual PK profiles, subjects will receive 6.6 mg/kg Plasminogen IV infusion every second, third, or fourth day for 12 weeks during Segment 2. Subjects will receive approximately 21 to 42 doses in Segment 2.

For subjects who do not participate in Segment 1 and directly enter Segment 2, baseline assessments will be conducted before the first dose of Plasminogen IV infusion, including a blood sample to measure the baseline plasminogen activity and antigen as well as D-dimer levels. Their dosing interval will be every second, third, or fourth day, depending on each subject's PK profile on file.

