3.6.2 Stopping Rules

Any subject who experiences any of the following occurrences will suspend the IMP treatment until further assessments:

- Anaphylactic response to study drug administration
- A significant AE that, in the investigator's opinion, necessitates suspension of treatment
- Confirmed presence of neutralizing antibodies (in at least 2 measurements) in association with diminished plasminogen activity that obviates the potential benefit of plasminogen replacement therapy.
- Thrombotic or uncontrolled bleeding event requiring hospitalization

The SMC will review safety data on an ongoing basis and will determine if a subject should stop treatment, or if there are unforeseen events (e.g., thromboembolic event) that would warrant halting or stopping the study. Such events will be discussed with FDA before enrolling further subjects.

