3.6.3 Withdrawal and Replacement of Subjects

Subjects will be withdrawn for the following reasons:

- The subject withdraws consent (no justification is required); and/or
- The subject develops a condition that in the investigator's opinion makes it medically necessary that the subject not continue in the study.

After a discussion between the investigator and sponsor, subjects may be withdrawn for the following reasons:

- An AE that in the investigator's or sponsor's opinion requires the subject be withdrawn from the study;
- Violation of eligibility criteria;
- Major protocol violations or deviations from the treatment plan (e.g., incorrect IMP administration);

- Lost to follow-up after all attempts at contacting the subject; and/or
- Death.

In all cases, the reasons for withdrawal will be recorded in the subject's source documentation and in the Case Report Form (eCRF). It is possible that some subjects may become lost to follow-up during the study. Every reasonable effort will be made to contact these subjects; all available efficacy and safety data collected for these subjects will be used, even if incomplete. Subjects withdrawn from the study may be replaced so that there are at least 10 evaluable subjects.

Subjects who do not meet the entry criteria at screening will be ineligible for treatment and will be deemed screen failures. Subjects who are screen failed will not receive IMP; therefore, no PK or safety data will be collected for these subjects, and only demographic information will be collected on the eCRF. Subjects who screen fail will be considered screened but not enrolled. A screen failed subject may re-enter the study if they pass the re-screening. Only subjects who qualify for treatment will be enrolled.

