6.3.2 Pharmacokinetic/Pharmacodynamic Analysis

The primary endpoint is the number and percentage of subjects who achieve the target plasminogen activity trough levels for at least 3 measurements in 12 weeks during Segment 2. Primary endpoint success is defined as at least 80% of evaluable subjects (i.e., 8 or more) achieving the target trough levels for at least 3 measurements in 12 weeks. The target trough level is defined as an increase in plasminogen activity level of at least an absolute 10% (10 U/dL) from the subject's individual baseline level. Baseline is defined as the plasminogen activity level measured before the first dose of IMP at Segment 1, Day -4 for subjects who undergo Segment 1 or at Segment 2, Day 0 for those who do directly enter Segment 2.

The secondary PK endpoints include individual PK profiles at the end of Segment 2, compared with their PK profiles at baseline, and trough plasminogen activity and antigen levels during Segment 2 and Segment 3.

Plasminogen activity and antigen levels will be presented by individual subjects and summarized descriptively (number of subjects, mean, standard deviation [SD], coefficient of variation [CV], median, minimum, maximum, geometric mean and associated CV). Individual and median profiles of the concentration-time data will be plotted using nominal times. Median profiles may be presented on both linear-linear and linear-log scales.

Standard PK parameters, including area under the curve (AUC), clearance (CL), mean residence time (MRT), volume of distribution (V_d) and terminal half-life ($t_{1/2}$) will be calculated using non-compartmental analysis and baseline-adjusted plasminogen activity levels derived from Segment

1 data and, if a subject is suspected to develop neutralizing antibody to the IMP, plasminogen activity levels at the end of Segment 2.

Additional PK compartmental analysis may be performed and best-fit model will be used for further individual PK prediction.

The summary statistics will include the number of subjects, mean, median, standard deviation, minimum, and maximum. The PK parameters will be summarized with the geometric mean and 95% confidence interval around the geometric mean

D-dimer is monitored as a potential pharmacodynamic marker to better understand if there is a relationship between the levels of D-dimer in subjects over time and the subject's potential response to therapy.

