6.4 Sample Size

Approximately 15 subjects with hypoplasminogenemia will be enrolled in this study to achieve at least 10 evaluable subjects. No formal calculation was made for sample size because of the rarity of the disease. The sample size is based on known patients who have hypoplasminogenemia.

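### The primary PK success proportion leaves out dosed subjects who do not finish Segment 2 or give fewer than 3 troughs, so the rule can overstate success, though little room for this remains in the trial as run

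*Protocol*

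**What the plan says.** The rule for the primary PK endpoint is in Protocol Section 6.3.2 and is repeated in the Synopsis: "Primary endpoint success is defined as at least 80% of evaluable subjects (i.e., 8 or more) achieving the target trough levels". Reaching target means at least 3 Segment 2 measurements that are 10 U/dL or more above the subject's own baseline.

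Two places define who enters the denominator. Section 3.1 says an evaluable subject is one who "completes Segment 2 of plasminogen replacement therapy (see below) of the study and provides at least 3 blood samples" for trough activity. Section 6.1 says of the PK population: "Includes subjects who have completed Segment 2 dosing and have provided sufficient samples for PK assessments". The second definition names no number of samples.

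Three other provisions bear on who drops out of that set:
- Section 3.6.3: "Subjects withdrawn from the study may be replaced so that there are at least 10 evaluable subjects".
- Section 3.6.2 lists, among the reasons to suspend treatment, "Confirmed presence of neutralizing antibodies (in at least 2 measurements) in association with diminished plasminogen activity".
- Section 6.2 rules out imputation.

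Nothing in the protocol scores a dosed non-completer as a non-achiever. The Full Analysis Set in Section 6.1 is defined through efficacy assessments and is not linked to this endpoint.

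**The concern.** The trial has one arm and no blinding, and no sample size was calculated. The fixed 80% threshold is therefore the whole test of the primary PK endpoint, and its denominator matters.

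Membership of that denominator can depend on the outcome. A subject whose treatment is suspended for neutralizing antibody with diminished activity, and not resumed, has probably failed on the variable being measured. That subject does not complete Segment 2, leaves the denominator and may be replaced. A subject with fewer than 3 troughs cannot have 3 qualifying troughs, so excluding such subjects can only remove non-achievers. In both cases the reported proportion would describe those who finished with enough samples and not those who were treated.

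**Working it through.** **Inputs**
- Threshold: 80% of evaluable subjects, glossed as 8 or more (Section 6.3.2).
- Size: about 15 enrolled, at least 10 evaluable (Section 6.4). The same section says "No formal calculation was made for sample size because of the rarity of the disease", so there is no alpha, power or null rate to reproduce.
- Scheduled troughs: Weeks 2, 4, 6, 8, 10 and 12, which is 6; extra samples are allowed (Section 3.1).
- Conduct: all 15 enrolled subjects had at least 48 weeks of treatment, and the first 10 to complete 12 weeks all reached target (Introduction, clinical experience; Section 1.3 in the table of contents).

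**1. The plan's own figure.** Achievers needed = smallest whole number not below 0.80 × n. For n = 10, 0.80 × 10 = 8, which matches the plan. For n = 15, 0.80 × 15 = 12. The gloss of 8 fits only n = 10, so I take the percentage as the rule.

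**2. How each kind of dosed subject is scored**

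| Subject | Plan's denominator | All-dosed denominator |
|---|---|---|
| A. Completes, 3 or more troughs, at least 3 on target | Achiever | Achiever |
| B. Completes, 3 or more troughs, fewer than 3 on target | Non-achiever | Non-achiever |
| C. Completes, fewer than 3 troughs | Dropped | Non-achiever |
| D. Does not complete, fewer than 3 on target | Dropped | Non-achiever |
| E. Does not complete, at least 3 on target | Dropped | Achiever |

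Dropping C and D raises the plan's proportion or leaves it unchanged. Dropping E loses an achiever and works the other way; on the trough schedule, E is possible from Week 6. Low troughs on continued dosing (B) are counted as failures under both rules.

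**3. Which rows are open in this trial.** Treatment for at least 48 weeks in all 15 subjects runs past the 12 weeks of Segment 2, so D and E appear empty and there was nobody to replace. The first 10 reached target, so they have at least 3 troughs each. Row C can hold at most 15 − 10 = 5 subjects. Each would have to lack at least 6 − 2 = 4 of the 6 scheduled troughs.

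**4. Size.** Let x be the achievers and d the subjects dropped under row C. The plan reports x/(15 − d); the all-dosed figure is x/15.
- Worst case, x = 10 and d = 5: 10/10 = 100% against 10/15 = 66.7%.
- One subject dropped, d = 1:
  - x = 14: 100.0% − 93.3% = 6.7 points
  - x = 12: 85.7% − 80.0% = 5.7 points
  - x = 10: 71.4% − 66.7% = 4.8 points

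**5. When the success call would differ.** All-dosed success needs 12 achievers, which is 2 of the 5 later subjects, so it fails only if at least 4 of those 5 are non-achievers. With 11 achievers and one subject dropped, the plan's rule fails too (11/14 = 78.6%). With two dropped it passes (11/13 = 84.6%). With 10 achievers it needs three dropped (10/12 = 83.3%; with two, 10/13 = 76.9%). The two rules therefore disagree only if at least 4 of the 5 later subjects failed and at least 2 of them were dropped for lack of samples.

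**The case against.** The strongest reply is that the protocol's own account leaves almost nothing for the rule to distort. Nobody left before Week 48, the first 10 subjects all succeeded, and missing at least 4 of 6 scheduled troughs is unlikely and need not depend on activity. Activity is also presented by individual subject (Section 6.3.2), so an exclusion would be visible. Changing the primary denominator after the 12-week result was analysed and submitted for licensing would be post hoc. All of this stands. It limits the size of the point and argues for an added analysis, not a replaced one.

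A reader might infer four stronger things that the documents do not support:
- **That the trial could pass with 8 of 10 evaluable, which is 8/15 = 53.3% of those dosed.** The rule as written permits this, but it cannot occur here: with 10 known achievers the floor is 10/15 = 66.7%.
- **That suspension for neutralizing antibody makes a subject non-evaluable.** Section 3.6.2 suspends treatment pending further assessment. The subject drops out of the count only if Segment 2 is not completed.
- **That failures in general leave the denominator.** Section 3.6.3 does not list a low trough as a reason for withdrawal, and subjects with low troughs who stay on dosing remain as failures.
- **That the bias is always upward.** Row E in the working is the counter-example.

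The objection does not remove the defect in the rule. The protocol itself fixes the denominator, so the matter is not simply left to the statistical analysis plan.

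**Conclusion.** The point holds as a weakness in a stated decision rule, with a small practical effect in this version. The primary PK proportion drops dosed subjects who do not complete Segment 2 or give fewer than 3 troughs, when they could be scored. This tends to overstate success. What remains open is exclusion of up to 5 later subjects for too few samples: 66.7% against 100% in the extreme case, and at most 6.7 points for one subject.

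This rests on the Introduction's account of conduct, on reading 48 weeks of treatment as completion of Segment 2, and on the percentage being the operative threshold. The protocol does not say how many of the 15 are evaluable, so the actual difference may be zero. Nothing here suggests that the reported result for the first 10 subjects is wrong.

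**What to change.** In Sections 6.1 and 6.3.2, add a second computation of the primary PK proportion:
- **Denominator:** every subject who received at least one dose of IMP, in Segment 1 or Segment 2 (15 as enrolled, where 80% needs 12).
- **Achievers:** those with at least 3 on-target Segment 2 troughs, whether or not they completed the segment.
- **Non-achievers:** everyone else, whatever the reason.
- **Replacements:** a replacement does not remove the withdrawn subject from the denominator.

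Report this beside the evaluable-set result, and state that it was added after the 12-week interim analysis.

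The cost is wording only. No new data are needed: troughs are already scheduled every 2 weeks, and Section 3.5.1.8 includes a trough at discontinuation. The later analyses in Section 6.5 can carry it. The downside is that the figure may be slightly less favourable. If all 15 subjects have enough samples, the two figures will agree, which would show that the result does not depend on selecting completers.
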